3.1.2 Intervention description: Touch - High/Low

The education and training intervention, referred to as Touch, was performed by trained Technology Navigators (TNs) who deliver training tailored to both the version of

ⁱ This function was automatic, so was not considered selectable and not included in the count of functions for either the Full- or Lite-Tech versions.

MyChart Bedside installed on their tablet (both Full- and Lite-Tech) and the perceived capacity of the patient.

Patients assigned to the Low-Touch intervention received an intervention focused on providing them with resources to conduct self-guided learning of MyChart Bedside. Specifically, TNs directed patients to the tutorial videos integrated in the MyChart Bedside application that explained the portal's functions.

In contrast, patients assigned to the High-Touch intervention would systematically review each of the functions of MyChart Bedside with the TN who would discuss how and when they are appropriately used. Patients were encouraged to use their tablet and follow along with the training as the TN moved through each function and ask the TN questions about their records during the presentation. The TNs tailored their presentation based on a patient's demonstrated knowledge of the technology to minimize patient participation burden while focusing on explaining the value of each function within the application. Patients unavailable after three intervention attempts were converted to Low-Touch.

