3.1.3 Allocation ratio

The Tech intervention contrasted two function sets—Lite-Tech (40% allocation), which was a minimalistic toolset focused on providing basic data to the patient, and Full-Tech (60% allocation), a more expansive toolset. The Touch intervention contrasted two training approaches—Low-Touch, a self-guided approach where patients could view built-in tutorials, and High-Touch (initially 50% allocation), where patients receive in-person guided training with the technology. The realized allocation ratios are presented in Table 2.

Table 2. Realized allocation ratio.

Tech Allocation	Touch Allocation		Total
	High	Low	
Full			
Frequency	624	1,523	2,147
Row %	29.1%	70.9%	100.0%
Column %	69.3%	76.5%	74.2%
Overall %	21.6%	52.7%	74.2%
Lite			
Frequency	277	468	745
Row %	37.2%	62.8%	100.0%
Column %	30.7%	23.5%	25.8%
Overall %	9.6%	16.2%	25.8%
Total			
Frequency	901	1,991	2,892
Row %	31.2%	68.8%	100.0%
Column %	100.0%	100.0%	100.0%
Overall %	31.1%	68.8%	100.0%

The assignment protocol used three phases where the Touch allocation ratio was changed by the research team.

1. In Phase 1, patients received the High-Touch intervention only after consenting to the study and submitting their Admission survey (see Section 3.8.2). Low-Touch patients could view the tutorial at any point and were not required to complete the Admission survey. Phase 1 assigned patients to High/Low-Touch in a 1:1 ratio.
2. In Phase 2, beginning in February 2018, the study shifted to a 3:1 ratio of High/Low-Touch. This change was done to ensure that sufficient individuals were assigned to the High-Touch intervention due to under-enrollment. Quality monitoring of the study found a number of exogenous factors that were impacting the High-Touch intervention, including, but not limited to: patient discharges; patient moved to other rooms; patient not present during TN rounding; patient was engaged with the care team and unable to work with the TN; and tablet returned prior to receiving an intervention. This change in the ratio was intended to increase the number of patients who would be eligible to receive a High-Touch intervention while maintaining the *per protocol* approach in that these exceptions were considered a component of the Protocol.

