3.4 Sample size

The study did not adopt a sampling frame and represented a census approach to the implementation. The Consort Diagram (see Figure 1), provides information on the pragmatic factors that limited enrollment.

The original protocol calculated power based on 2016 Hospital Consumer Assessment of Healthcare Provider and Systems (HCAHPS) patient satisfaction scores as a baseline for outcome measures using G*Power 3.1 software. An expected enrollment of 3,872 was planned with the design expected to be sensitive enough to identify changes of between 2.2% and 3.8% across the panel of HCAHPS patient satisfaction scores.

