6.3.10 Missing Touch intervention date

The date of receipt of a High-Touch intervention was supposed to be recorded for each patient in Qualtrics in an administrative data system. In rare instances, this date was missing. For these instances, intervention delivery date was identified from study notes made by the TNs about patient visits that included dates and details of encounters and was entered manually.

Section 7: References

4. US Department of Health Human Services. Multiple chronic conditions—a strategic framework: optimum health and quality of life for individuals with multiple chronic conditions. Washington, DC: US Department of Health and Human Services 2010;2.

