## Section 1: Statistical analysis

### 1.1 Confidence intervals and p-values

For all statistical tests, a p-value of 0.05 was used to assess significance and 95% confidence intervals were reported. No adjustment was done for multiple hypothesis testing.

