#### 1.5.1 Outcome 1 – Number of MyChart Bedside sessions within the enrollment admission was dependent on treatment

*Dependent variable specification:* The count of MyChart Bedside sessions for the admission associated with study enrollment.

- Enrollment admission was defined as the admission when the patient was enrolled in the study.

*Statistical model:* Negative binomial model with non-interacted and interacted study arms as binomial predictors.

---

ii Preliminary analysis of adoption rates for the outpatient portal revealed a rapid decrease in the numbers following the first few months, which motivated us to set the value for the cutoff date at 90 days in order to more conservatively attribute portal use to an individual's participation in the study.

*Covariates:* No covariates were added to this analysis.

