### 1.5.2 Outcome 2 – Comprehensive use was dependent on treatment

*Dependent variable specification:* A binary variable identifying participants that used all available functions based on their Tech arm assignment (1 = comprehensive functions user; 0 = not a comprehensive functions user).

- The definition of “comprehensiveness” was tested in two different ways:
  - **Definition 1: Based on use of all available functions:** Users were considered comprehensive functions users when they reached a threshold number of functions used based on their Tech Arm. For Lite-Tech users, this threshold was three selectable functions available—Bedside Tutorial, Dining on Demand, and To Learn. For Full-Tech users, this threshold was eight of the 10 functions available, including the three functions available to Lite-Tech users.
  - **Definition 2: Based on use of the functions available to all users:** Users were considered comprehensive functions users when they used the three functions that were available to all users.

*Statistical model:* Logistic regression model with non-interacted and interacted study arms as binomial predictors.

*Covariates:* No covariates were added to this analysis.

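### Activity logged during the High-Touch training visit counts toward comprehensive use, so a positive Touch result on H1 Outcome 2 may only show that the training was delivered

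*SAP*

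**What the plan says.** Protocol 3.1.2 describes High-Touch as a function-by-function review with a navigator: "Patients were encouraged to use their tablet and follow along with the training as the TN moved through each function". The visits were tailored to what the patient already knew. Low-Touch patients were pointed to the built-in tutorial, which is one of the three functions that every patient has.

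The H1 outcomes draw on logged activity over the whole enrollment admission:

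- **Outcome 1 (SAP 1.5.1):** "The count of MyChart Bedside sessions for the admission associated with study enrollment".
- **Outcome 2 (SAP 1.5.2):** Definition 1 requires three of three functions in Lite-Tech or eight of ten in Full-Tech. Definition 2 is: "Users were considered comprehensive functions users when they used the three functions that were available to all users". Neither sets a minimum number of uses or asks for separate sessions.
- **Outcome 3 (SAP 1.5.3):** each function's share of all the patient's actions, in Full-Tech only.

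The removal rules cover actions outside the encounter (Protocol 6.3.4), passive actions (Protocol 6.3.5), and sessions without an active task and repeated logins (SAP 1.4.5). Participants with no portal use in the enrollment admission are excluded (Protocol 6.3.8, item 4).

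The training date is held in principle: "The date of receipt of a High-Touch intervention was supposed to be recorded for each patient in Qualtrics", with gaps filled from navigator notes (Protocol 6.3.10). No H1 outcome uses it.

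**The concern.** The training visit takes place inside the encounter, on the tablet whose log supplies the outcome, and it goes through the same list of functions that the outcome checks off. None of the removal rules touches it. A patient who follows the walk-through once and never opens the portal again could be scored as comprehensive. A Low-Touch patient has no such prompt beyond the tutorial.

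H1 is a primary hypothesis about patients' use of the portal. If the outcome can be met by delivering the intervention, a significant Touch coefficient, or a Tech-by-Touch term, does not show that training changed what patients do on their own. The same activity enters the Outcome 3 shares and would pull them toward the pattern of the training.

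**Working it through.** **The plan's own figures.** The only sizing statement is "An expected enrollment of 3,872 was planned", expected to "identify changes of between 2.2% and 3.8% across the panel of HCAHPS patient satisfaction scores" (Protocol 3.4). It concerns satisfaction, not portal use. Power and baseline rates are not given, so it cannot be reproduced strictly, but it is plausible: at 1:1, two-sided 0.05 and 80% power, 3,872 patients detect 3.79 points at a 75% baseline, 2.54 at 90% and 2.13 at 93%. The documents give no H1 figure to reproduce.

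**Inputs.**

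- "The realized allocation ratios are presented in Table 2" (Protocol 3.1.3): High 901, Low 1,991, total 2,892, and 901/2,892 = 31.2%.
- Touch was allocated 1:1 and later 3:1, so at least half should have been assigned High. I therefore read Table 2 as showing the intervention received, which the protocol does not state.
- Protocol 4.3 reports 3 patients moved from Low to High, so 901 − 3 = 898 of those assigned High were trained.
- Significance: "a p-value of 0.05 was used to assess significance and 95% confidence intervals were reported" (SAP 1.1), taken as two-sided, so 0.025 in the direction of High-Touch.
- Assumed: true comprehensive rate b of 5-30% in both arms; a share f of trained patients, not otherwise comprehensive, for whom the walk-through completes the set; ordinary standard errors instead of hospital-clustered ones; no effect on own use.

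**Outcome 2, intention to treat.** Trained share among those assigned High: t = 898/(2,892 × 0.50) = 0.621, or 898/(2,892 × 0.75) = 0.414. High-Touch rate = b + (1 − b) × t × f. The log odds ratio against b is tested with a Wald test, and P = Φ(log OR/SE − 1.96).

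Example with b = 15%, f = 10% and a 50% split: 0.15 + 0.85 × 0.621 × 0.10 = 0.203; OR 1.44; SE 0.0985; P = Φ(3.71 − 1.96) = 0.96. At a 75% split, OR is 1.29 and P is 0.57.

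Across b = 5-30%:

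| f | OR, 50% High | P | OR, 75% High | P |
|---|---|---|---|---|
| 5% | 1.1-1.6 | 0.24-0.89 | 1.1-1.4 | 0.11-0.46 |
| 10% | 1.2-2.3 | 0.71-1.00 | 1.1-1.9 | 0.30-0.92 |
| 25% | 1.6-4.7 | 1.00 | 1.4-3.3 | 0.94-1.00 |

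**Outcome 2, grouped by receipt (Protocol 4.3).** Here nothing dilutes the effect. With 901 v 1,991, the probability of significance reaches 80% when f is 1.9% (b = 2%), 2.8% (5%), 4.0% (10%), 5.8% (20%) or 9.3% (40%).

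**Outcome 1.** Suppose the visit adds one session to a negative binomial count with mean m (5 or 10) and dispersion a (0.8-1.2). Ignoring the zero-use exclusion, the rate ratio is (m + t)/m = 1.04-1.12. With the exclusion, let z = (1 + am)^(−1/a) be the share who would have no use. Low-Touch loses all of them, while High-Touch keeps those who were trained. The rate ratio becomes (m + t)(1 − z)/{m[1 − (1 − t)z]}. This is exactly 1.00 at a = 1, 1.01-1.03 at a = 0.8 and 0.98-0.99 at a = 1.2.

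**The case against.** The strongest reply is that the mechanism is inferred. Protocol 6.3.5 does not list the active actions, and its one example is sending a message, which completes a task. If Dining on Demand is logged only when food is ordered, a walk-through without an order satisfies neither definition. Following along was encouraged, not required, and visits were tailored. All of this stands: f is unknown and could be near zero. It limits how firmly the size can be stated, but it does not supply the missing rule.

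A reader might infer that the session count is inflated in the same way. The documents do not support that. A new session needs a login or a 15-minute gap (SAP 1.4.5), and both arms were guided to consent inside the portal (Protocol 5.2.1), so training at first contact may fall within a session that both arms log. The zero-use exclusion also removes nearly all of the bias in the model above. If would-be non-users are rarer than that model implies, some inflation remains, but no false-positive rate for sessions can be claimed.

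A reader might also extend the point to the Tech effect. It does not reach that far, because both Tech versions received training tailored to them.

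H1 can be read as total use, training included. On that reading the all-use result is a legitimate description, but it is not evidence that training changed patients' own use.

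The inputs b and f have no source in the documents, and 0.30-1.00 is a wide range. The Outcome 2 figures also leave out the zero-use exclusion. It keeps some trained would-be non-users in the High-Touch denominator, which is a partial offset. Clustering by hospital is ignored too.

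**Conclusion.** The point holds for Outcome 2, under both definitions, and in lesser form for the Outcome 3 shares. As specified, the Touch contrast on comprehensive use mixes delivery of the training with its effect. Intention to treat dilutes this and does not remove it. The SAP's per-protocol set and the protocol's regrouping by receipt give it full weight, and those two documents' analysis populations need to be reconciled in any case.

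The size depends on a quantity that only the logs can supply. If the walk-through completes the set for as few as 5% of trained patients, the probability of a significant result favouring High-Touch is 0.11-0.89 instead of 0.025. At 25% it is at least 0.94. These figures assume 898 trained of 2,892, true rates of 5-30%, ordinary standard errors and no effect on own use. For session counts the illustrated rate ratio is about 0.98-1.03, which supports no claim in either direction.

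**What to change.** First check in the logs which walk-through actions are classed as active. Then add to SAP 1.5.2 and 1.5.3 a version of the outcome that leaves out navigator-visit activity and gives both arms the same observation window:

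- Where visit times are held, drop only the sessions that overlap a navigator visit, in either arm.
- Where only the date is held, drop that day in High-Touch and a matched day (same day since consent) in Low-Touch.
- Keep the analysis set, including the zero-use exclusion, as in the all-use analysis, so that dropping days does not select patients.
- Report this version beside the all-use result, and claim a Touch effect on comprehensive use only if it holds here.

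Do not drop an extra day in High-Touch alone. Suppose the contact day is dropped in both arms, each common function is used with daily probability 0.3, and half of trained patients are trained on a separate day. The chance of using all three functions in k days is (1 − 0.7^k)³. With 3 tablet-days and a 50% split, Low-Touch is 0.51³ = 0.133. High-Touch is 0.6895 × 0.133 + 0.3105 × 0.027 = 0.100, so the OR is 0.73. With 8 tablet-days and a 75% split it is 0.91. Both are false effects against High-Touch.

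The cost is SAP wording and a re-run on data already held. Some genuine same-day use is lost, with a little less precision. Trained patients whose only use was the visit stay in High-Touch with no Low-Touch counterpart, which leans slightly against High-Touch and should be stated.

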### 1.5.3 Outcome 3 – MyChart Bedside use (by function) was dependent on Touch arm.

*Sub-sample specification:* As a function of the hypothesis and outcome specification, this analysis was not subject to sub-sample analysis as described in section 1.4.2. This analysis only used the Full-Tech arms, and therefore only used the Touch predictor in the statistical model.

*Outcome specification:* Proportion of total use, calculated for each user by dividing the sum of actions in a given function from the total sum of user actions during their enrollment admission accounted for by each function.

*Statistical model:* For each function, a fractional logistic regression model was performed, with use proportion as the response variable and Touch status as the explanatory variable.

*Covariates:* No covariates were added to this analysis.

## 1.6 Hypothesis 2: Patient satisfaction and involvement

*H2: Individuals assigned to the High intervention levels for Tech and Touch will demonstrate higher levels of satisfaction with (H2a) and involvement in (H2b) their care experience.*

Questions from the satisfaction and experience domains of the Admission, 15-day, and 6-month Post-discharge surveys were used to test H2. Below we describe the specific questions that were included in these analyses and how these outcomes were specified and tested.

### 1.6.1 Outcome 1 – Patient satisfaction was dependent on treatment

*Outcome specification:* Variations of this outcome were available in each survey. The following 5-point Likert scale survey items were explored as individual items dichotomized to one “most positive” response versus all other responses:

- **15-day Post-discharge survey:** In your most recent hospital experience, how satisfied were you with the interactions you had with your healthcare professionals?
- **15-day Post-discharge survey:** In your most recent hospital experience, how satisfied were you with how well your healthcare professionals responded to your concerns?
- **6-month Post-discharge survey:** In the past six months, how satisfied were you with the interactions you had with your healthcare professionals?
- **6-month Post-discharge survey:** In the past six months, how satisfied were you with how well your healthcare professionals responded to your concerns?

*Statistical Model:* Logistic regression models with and without an interaction of Tech and Touch were reported.

*Covariates:* The corresponding survey item from the Admission Survey was used as a covariate for the items listed above. The two relevant survey items were:

- **Admission survey:** In the past 12 months, how satisfied were you with the interactions you had with your healthcare professional?
- **Admission survey:** In the past 12 months, how satisfied were you with how well your healthcare professionals responded to your concerns?

*Sub-sample analysis:* No sub-sample analyses were considered for this outcome.

### 1.6.2a Outcome 2a – Patient involvement was dependent on treatment

*Outcome specification:* In the 15-day Post-discharge survey, the following 5-point Likert scale survey items were explored as individual items dichotomized to one “most positive” response versus all other responses:

- **15-day Post-discharge survey:** All of my questions about managing my health, including my medications, were addressed before I left the hospital.

*Statistical Model:* Logistic regression models with and without an interaction of Tech and Touch were reported.

*Covariates:* No covariates were added to this analysis.

*Sub-sample analysis:* No sub-sample analyses were considered for this outcome.

### **1.6.2b Outcome 2b – Patient involvement was dependent on treatment**

*Outcome specification:* In the 15-day Post-discharge survey, a binary variable identifying whether the participant marked the item:

- **15-day Post-discharge survey:** If you had a question about your care while you were in the hospital, what steps did you take to find an answer? (mark all that apply)
  - I asked my doctor
  - I asked a nurse
  - I asked another hospital staff member
  - I searched online
  - Other
  - I did not have questions
- **15-day Post-discharge survey:** What kinds of activities did you use the tablet for? (mark all that apply)
  - Email
  - Research health issues
  - Social media
  - Watch movies/ TV
  - Communicate with my family
  - Play games
  - MyChart Bedside
  - None of the above

*Statistical Model:* Logistic regression models with and without an interaction of Tech and Touch were reported.

*Covariates:* No covariates were added to this analysis.

*Sub-sample analysis:* No sub-sample analyses were considered for this outcome.

## 1.7 Hypothesis 3: Outpatient portal adoption and use

*H3: Individuals assigned to the High intervention levels for Tech and Touch will demonstrate higher rates of outpatient portal adoption (i.e., of Epic's MyChart) for those admitted without prior outpatient portal use (H3a), and higher use of MyChart for those admitted who had previously used the outpatient portal (H3b).*

MyChart adoption was inferred by evidence of use of the application and timed around the first recorded session for each individual. Study participants were classified into one of four groups, based on the presence of non-zero length sessions associated with the participant's usage of MyChart prior to enrollment in the study.

- **Group 1 – Prior MyChart User:** A record of MyChart sessions prior to study enrollment.
- **Group 2 – New MyChart User:** No record of MyChart sessions prior to study enrollment and a record of subsequent MyChart use within the cutoff period.
- **Group 3 – Never MyChart User:** No record of MyChart sessions prior to study enrollment and no record of subsequent MyChart use within the cutoff period.

MyChart frequency of use indicated the number of MyChart sessions (see section 1.4.5.) on record for a given study participant. The number of MyChart sessions that occurred before the cutoff date (see section 1.4.7) was used to quantify MyChart frequency of use.

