2.2 Objectives

The ***High Tech and High Touch (HT2): Transforming patient engagement throughout the continuum of care by engaging patients with portal technology at the bedside*** study at OSU Wexner Medical Center (OSUWMC) sought to study how the deployment of a commercial (i.e., Epic Systems) inpatient portal, MyChart Bedside, impacted identified patient outcomes. To evaluate the impact of function set and training

on inpatient (i.e., MyChart Bedside) and outpatient (i.e., MyChart) portal use, the HT2 Study²⁰ was designed as a large-scale, pragmatic randomized controlled trial across six hospitals in a healthcare system.

Using a two-by-two factorial design, HT2 simultaneously examined the effects of two approaches to portal training with two versions of the inpatient portal. HT2 was designed to test four study hypotheses:

Hypotheses related to primary outcomes:

H1: Patients assigned to the High intervention levels for Tech and Touch will demonstrate higher use of MyChart Bedside.

H2: Patients assigned to the High intervention levels for Tech and Touch will demonstrate higher levels of satisfaction with (H2a) and involvement in (H2b) their care experience.

Hypotheses related to secondary outcomes:

H3: Patients assigned to the High intervention levels for Tech and Touch will demonstrate higher rates of outpatient portal adoption (i.e., of Epic's MyChart) for those admitted without prior outpatient portal use (H3a), and higher use of MyChart for those admitted who had previously used the outpatient portal (H3b).

H4: Patients assigned to the High intervention levels for Tech and Touch will demonstrate higher levels of self-efficacy.

To prevent outcome reporting bias and data-driven analysis of results, we produced this detailed statistical analysis plan. The plan was originally developed and drafted prior to examination of the data, and in the absence of randomization knowledge. The plan has been revised as the analysis has proceeded.

Section 3: Study methods

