3.1.1 Intervention description: Tech - Full/Lite

The Full-Tech intervention consisted of the standard build of the MyChart Bedside product as delivered from Epic and augmented by OSUWMC at the start of the study. The application was served by a *Home* landing page that displays events scheduled for the day and recent health updates and included access to 10 additional functions located in tabs along the side of the inpatient portal image:

1. *Home*: presented events scheduled for the day and data on patient vitals, including last blood pressure reading, current pulse and other patient vital signs refreshed from the Electronic Health Record (EHR) once every 5 minutesⁱ
2. *Bedside Tutorial*: tutorial materials for the use of MyChart Bedside, including an 11-minute video explaining how to use MyChart Bedside and access to PDF versions of tutorial materials
3. *Dining on Demand*: food ordering service
4. *To Learn*: educational resources for the patient based on their treatment plan
5. *Happening Soon*: a timeline for the care activities that the patient could expect for the day
6. *Taking Care of Me*: information detailing members of the patient's care team
7. *Messages*: non-urgent secure messaging with the patient's care team
8. *My Health*: recent vital signs and lab test results
9. *Notes*: write/record reminders and notes
10. *I Would Like*: non-urgent requests from pastoral care or gift shop
11. *OSU MyChart*: allowed the patient to access MyChart, including creating a new account

In addition to the *Home* landing page, the Lite-Tech version of MyChart Bedside consisted of the 3 functions: *Bedside Tutorial*, *Dining on Demand*, and *To Learn*.

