5.2 Recruitment

The AMC Epic Clarity tables were used to develop a fully identified custom Census Report which provided information on all patients who met the inclusion criteria present in the hospital at midnight of each day. The research team integrated this report with the study database to create a daily list of individuals that had consented, refused, not been provided a tablet, or were eligible for being visited by a TN during TN rounding. This information was used to set up a rounding schedule to visit the rooms of these patients to follow up about study participation as follows:

1. In cases where a patient had not been provisioned and there were no clinical notes detailing a rationale for the withholding of access, members of the research team would approach the nursing team and ask them to make a formal determination about the appropriateness of the tablet for the patient.
2. In cases where a patient was provisioned, the study team would put the patient on the rounding schedule and attempt to recruit them to the study.

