### 1.7.1 Outcome 1 – MyChart adoption among participants without outpatient portal usage prior to enrollment was dependent on treatment

*Outcome specification:* A categorical variable identified whether the participants used the portal before the end of the cutoff period (1 = Admission New User or Post-Discharge New User; 0 = Never MyChart User). Prior MyChart Users were not included in the analysis for this outcome.

*Statistical model:* Logistic regression model with non-interacted and interacted study arms as binomial predictors.

*Covariates:* No covariates are added to this analysis.

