### 1.7.5 Outcome 5 – Frequency of use for Prior MyChart Users

*Outcome specification:* The count of MyChart sessions occurring between the date of enrollment in the study and the cutoff date. This variable was specified as a count variable. New MyChart Users and Never MyChart Users were not included in the analysis for this outcome.

*Statistical model:* Negative binomial regression model for counts of sessions with non-interacted and interacted study arms as binomial predictors (see Equation 4).

Equation 4: If Prior MyChart User =1;  $y = X_{Tech} + X_{Touch} + X_{Tech*Touch}$

*Covariates:* The count of pre-enrollment sessions was included as a covariate in the model to control for previous use.

*Sub-sample analysis:* No sub-sample analyses were considered for this outcome.

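### SAP 1.7 groups patients for H3 by MyChart use before study enrollment, after Tech exposure has begun, while other passages point to admission; the conflict could bias the H3a Tech odds ratio against Full-Tech

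*SAP*

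**What the plan says.** Protocol 2.2 states the adoption hypothesis "for those admitted without prior outpatient portal use (H3a"), and H3b for those admitted as existing users. SAP 1.7 repeats this and then builds its groups on a different time point. Group 1 (Prior) is "A record of MyChart sessions prior to study enrollment". Group 2 (New) is "No record of MyChart sessions prior to study enrollment and a record of subsequent MyChart use within the cutoff period". Group 3 (Never) also looks back from enrollment. SAP 1.7.1 keeps that anchor in its title, "MyChart adoption among participants without outpatient portal usage prior to enrollment was dependent on treatment", and states that "Prior MyChart Users were not included in the analysis for this outcome".

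For existing users, SAP 1.7.5 counts sessions from the enrollment date and adds that "The count of pre-enrollment sessions was included as a covariate in the model to control for previous use".

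Two other places use a different anchor. SAP 1.4.8 measures both cutoffs from the hospital encounter in which the patient was enrolled. SAP 1.7.3 is titled for people who started MyChart during the enrollment admission, which SAP 1.5.1 defines as the whole admission.

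On the intervention, Protocol 3.1.1 lists an OSU MyChart function in Full-Tech that "allowed the patient to access MyChart, including creating a new account". The three Lite-Tech functions do not include it. On timing, Protocol 5.2 says: "In cases where a patient was provisioned, the study team would put the patient on the rounding schedule and attempt to recruit them to the" […].

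**The concern.** A stratum used to compare randomised arms should be fixed before the treatment can act. Here the Prior/New/Never split is made at enrollment, when the tablet version has already been assigned and is in use. Full-Tech offers a direct route into MyChart and Lite-Tech does not, so Tech itself can move a patient from New to Prior.

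In H3a that would remove some of the quickest Full-Tech adopters from both numerator and denominator. In H3b it would add new adopters to the Full-Tech prior-user group and put sessions that Tech may have caused into the baseline covariate. Analysing by randomised arm (SAP 1.4.1) does not repair this, because the subset being analysed would itself depend on the arm.

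**Working it through.** **Step 1: order of events.**
- Tech follows the last four MRN digits, set before study assignment (Protocol 3.2.1).
- Nursing staff provision the tablet as hospital practice (5.1), and only provisioned patients are included (5.1.1).
- Provisioned patients are then approached (5.2) and normally consent through a link inside MyChart Bedside (5.2.1).
- The Admission survey is described as taken at enrollment (3.8.2) and immediately after consent (5.2.1), so enrollment means consent.
- The inclusion criteria in 5.1.1 set no limit on the time from admission or provisioning to consent.

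**Step 2: where a pre-consent starter goes.** Take a patient with no MyChart use at admission whose first session falls between provisioning and consent.

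| Passage | Anchor | Placement |
|---|---|---|
| Protocol 2.2, H3 | admission | H3a, adopter |
| SAP 1.7 groups, 1.7.1 | enrollment | Prior User: out of H3a, into H3b |
| SAP 1.4.8 | hospital encounter | New User |
| SAP 1.7.3 title | enrollment admission | Admission New User, but excluded if Group 1 applies |

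SAP 1.7 announces four groups and lists three. Admission New User and Post-Discharge New User, used in 1.7.1 to 1.7.3, are not defined.

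**Step 3: effect on the H3a odds ratio.** The plan gives no H3 rate, sample size or power, so there is no figure to reproduce. In one arm, let p be true adoption among patients without use at admission, and f the share of those adopters who start before consent. Never Users stay at 1 − p and counted adopters fall to p(1 − f), so the observed odds are p(1 − f)/(1 − p). Taking the ratio of arms:

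OR_observed = OR_true × (1 − f_Full)/(1 − f_Lite).

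**Step 4: numbers (all f and p are assumptions).**
- f_Full = 5%, 10%, 20%, 30% with f_Lite = 0 gives multipliers of 0.95, 0.90, 0.80, 0.70.
- f_Full = 20% with f_Lite = 10% gives 0.80/0.90 = 0.89. Equal f gives 1.
- True adoption of 25% against 20% gives OR (0.25/0.75)/(0.20/0.80) = 1.33. With f_Lite = 0, f_Full = 10%, 20%, 30% gives 1.20, 1.07, 0.93.

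**Step 5: scale.** Protocol Table 2 has 2,147 Full-Tech and 745 Lite-Tech participants. Assume half had no prior use (about 1,074 and 373), 20% adoption in both arms, and f_Lite = 0. The calculation is a two-sided 5% two-proportion test with pooled variance, ignoring hospital clustering and the offset.

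| f_Full | Full-Tech adopters moved | Chance of a significant result against Full-Tech |
|---|---|---|
| 0 | 0 | 2.5% |
| 5% | 11 | 5% |
| 10% | 21 | 11% |
| 20% | 43 | 31% |
| 30% | 64 | 62% |

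At f_Full = 10%, varying adoption over 10–30% and the no-prior-use share over 30–70% gives about 6–16%. With a real effect of 28% against 20% (OR 1.56), power is about 87% at f_Full = 0, then 77%, 63% and 31% at 5%, 10% and 20%.

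**Step 6: other H3 outcomes.** SAP 1.7.2 is unchanged, because these patients are outside it under either anchor. SAP 1.7.3 has fewer adopters in its numerator, so the same pre-consent starters are at least as large a share of it. With f_Lite = 0 its multiplier is no closer to 1 than in 1.7.1.

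**The case against.** The strongest reply is that the analysts may have used an admission anchor throughout. SAP 1.4.8 uses pre-study enrollment for a cutoff that it then measures from the hospital encounter, 1.7.3 names starters during the enrollment admission, and the hypothesis speaks of admission. SAP 1.7 also refers to a cutoff section, although the number it cites (1.4.7) is the Likert section and the cutoff stands in 1.4.8. On this reading pre-consent starters are Admission New Users and the problem largely disappears. This stands as a possible reading. It does not settle the matter, because the Group 1 to 3 definitions and the 1.7.1 title say enrollment.

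Three limits on size also stand. The documents give neither the interval from provisioning to consent nor the number of sessions within it. Lite-Tech patients could reach MyChart on another device, and only the difference between arms biases the contrast. That sessions opened from the Bedside tab appear in the MyChart log is an inference. Large distortions also need large shares: at 30% adoption in both arms, an odds ratio of 0.67 requires one third of Full-Tech adopters to have started before consent.

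A reader might infer that H3b is biased against Full-Tech too, because recent adopters are lighter users. Nothing in the documents supports that. SAP 1.7.5 adjusts for earlier sessions, and a new adopter with a low baseline count may show high later use for that baseline, which would push the adjusted effect the other way.

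**Conclusion.** The SAP uses conflicting anchors for prior MyChart use, and the one in its operative group definitions falls after Tech exposure begins. Under that wording Tech can change who belongs to H3a and H3b and can change the 1.7.5 covariate. If pre-consent starts are commoner in Full-Tech, the H3a Tech odds ratio is biased against Full-Tech by the factor in Step 3. The size is unknown, and the figures above are illustrations only.

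It would go too far to conclude that the Tech contrast has been shown to be biased, or that the trial's randomised comparison fails. The first depends on which anchor was applied and on a count that is not reported. The second is not supported: this route concerns H3 alone, which is secondary, and H1, H2 and H4 do not use these groups. The Touch contrast is not affected by this route because Touch training follows consent. The change should be made; it is not critical to the trial as a whole.

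**What to change.** Use one anchor in SAP 1.7: the start of the enrollment admission in the merged ADT record (Protocol 6.3.2). Apply it to all of the following:
- the Prior, New and Never groups;
- the prior-session covariate in 1.7.5;
- the start of the session counts in 1.7.4 and 1.7.5. If only the covariate were moved, sessions between admission and consent would fall in neither covariate nor outcome.

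Define Admission New User as a first session from admission to discharge, including before consent, and Post-Discharge New User as a first session from discharge to the cutoff. Align 1.4.8 and the cross-references in 1.7. Report the number of first sessions between admission and consent by Tech arm, which shows directly how much the choice of anchor matters.

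Tech follows the MRN, so an earlier stay with a tablet could also create a Prior User. Handle randomised patients with such a stay in a sensitivity analysis that excludes patients placed in Full-Tech without randomisation (Protocol 3.2.1, 4.2.1). Moving the main anchor back to first provisioning is not advisable, because it could credit pre-study adoption by those non-randomised patients to Full-Tech.

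The cost is SAP wording, a re-run of the H3 models and one small table. Encounter times and timestamped MyChart sessions are already held (Protocol 3.8.1, 6.2). The encounter and Bedside tables cover the study period, so the sensitivity analysis may not reach stays before it without a further data pull.
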